In addition to the RCT, the project group will write up on an extended naturalistic cohort study initiated after the previous pilot, and investigate this cohort in relation to similar aims as described above.

Inclusion criteria

Patients with a substance use disorder referred to outpatient addiction treatment, aged >18 of both genders.

Exclusion criteria

Severe psychiatric disorders (e.g. psychosis) that have not been stabilized with e.g., medication (assessed as a part of the clinical process at the clinic). Severe cognitive impairment or language problems (inability to converse for interviews).

Experimental design

The proposed experimental study will have a two-group pre-post design with an intervention group (NF+TAU) and a control group (TAU). Participants will include patients referred to outpatient addiction treatment at two clinics within Sørlandet Hospital HF, in Kristiansand and in Arendal. Because regular attendance is desirable for participation in the project, certain clinical selection criteria will apply, but this will be handled not by the project group itself, rather it will reflect ordinary practice within the present clinical setting. Thus, patients are thought to be clinically eligible to the NF condition after having achieved an initial level of stable attendance at the clinic. This is congruent with the study's focus on relapse prevention.

Patients meeting the criteria for inclusion will be informed about the project and given the opportunity to participate. After providing written, informed consent, those patients who choose to participate will be randomly assigned to either NF training + TAU, or TAU alone. The allocation will be determined through notes prepared in sealed envelopes by an external researcher based on a block randomization design. As a part of the NF+TAU condition, participants will be invited to an informal dialogue session within a month of starting the intervention, in which a user representative will be available to answer potential questions and share individual experience concerning the treatment. The TAU participants will receive standard psychotherapeutic treatment, chosen according to individual needs and therapist preference.

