Preliminary clinical experience indicates that the method represents an intriguing, technology-intensive option and a refreshing alternative for a treatment-fatigued patient population, resulting from offering traditional "talk therapies" only. The proposed study will provide new knowledge about the use of neurofeedback in the treatment of SUD, specifically the novel infra-low training methods, potentially leading to a more holistic treatment approach, improved retention and relapse rates, and reduced detrimental outcomes for a vulnerable and difficult to treat group of patients.

Environmental impact

The study is not expected to constitute any additional hazard to the environment.

Ethical perspectives

Participants will be included after they have provided written informed consent to join the study. Approval has been sought from the Regional Ethics Committee. Based on six years of clinical experience and the outcome of the 2012 pilot study, no adverse side effects are expected for the patients. In order to secure equal treatment to all participants, the TAU group will be offered NF after

study completion. The project group has decided against including a placebo control in the study, as the practice of offering 20 sessions of non-active feedback was deemed unethical.

Gender issues

Participants of both genders will be included, and it is expected that the sample will mirror the typical gender distribution of patients referred to addiction treatment. A female clinician with a master's degree will be engaged as clinical coordinator for the study and will be the natural candidate for the doctoral research fellowship position.

Dissemination and communication of results

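### Block randomisation by pre-prepared envelopes in an open-label trial with clinic-judged entry leaves early opening and guessing of assignments unexcluded

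*Combined protocol and SAP*

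**What the plan says.** Section 2, Experimental design, describes the allocation in one sentence: "The allocation will be determined through notes prepared in sealed envelopes by an external researcher based on a block randomization design". Consent comes first: "After providing written, informed consent, those patients who choose to participate will be randomly assigned".

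The same section leaves entry to the clinics. It says that "certain clinical selection criteria will apply, but this will be handled not by the project group itself", and that "patients are thought to be clinically eligible to the NF condition after having achieved an initial level of stable attendance at the clinic". No number of visits or length of time defines that level. Recruitment runs at "two clinics within Sørlandet Hospital HF, in Kristiansand and in Arendal".

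There is no sham arm. Section 4, Ethical perspectives, states: "The project group has decided against including a placebo control in the study". The same paragraph offers NF to the TAU group once the study is over.

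The primary outcome is the self-reported QoL-10, which is part of the baseline inventory (Instruments). The Statistics paragraph names Student's t-test for it. It names no baseline covariate and does not say whether follow-up or change scores are compared. Follow-up interviewers are blinded.

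The text does not state the block size, whether block sizes vary, whether each clinic has its own list, who holds and opens the envelopes, or who is kept unaware of the block scheme.

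**The concern.** Two routes to selection at entry stay open.

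- **Early opening.** External preparation conceals how the list was made. It does not by itself prevent an envelope from being opened before a patient is put forward.
- **Guessing.** Every completed block is balanced, so the arm that is behind is the likelier next assignment. Because treatment is open, anyone who knows the running counts can use this without knowing the block size.

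Either matters only if someone can choose whom to put forward, and when. A threshold described as "after having achieved an initial level of stable attendance at the clinic" allows that choice without breaking a rule. Clinic selection before a concealed allocation would affect generalisability only; together with foreseeable allocation it can bias the comparison. The unit already offers NF and reports favourable experience with it (section 2, Background), so indifference to allocation cannot be assumed. Blinded interviewers act after enrolment and cannot repair a difference created at entry. A positive result on a subjective endpoint would then be hard to defend, and concealment cannot be restored after recruitment.

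**Working it through.** **Inputs from the plan** (Sample size calculation; Statistics): SD 0.17, target difference 0.10, 40 analysed per group, two-sided alpha 0.05, t-test.

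**Assumptions** (not in the plan):
- block size b;
- mean QoL of the entrant shifted by +e when NF is guessed, by −e when TAU is guessed, and by nothing when the counts are tied;
- t-test on follow-up scores;
- no true NF effect.

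The plan gives no figure on predictability to reproduce. Its 40 / (1 − 0.20) = 50 per group is correct. Power at 40 per group comes out at about 74%, not 80%. That is a separate matter; 40 is only an input here.

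**1. Assignments known with certainty**, if the fixed block size is known: 2/(b + 2), that is 50% for b = 2, 33% for b = 4 and 25% for b = 6.

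**2. Correct guesses** (c) from the rule that the arm behind comes next, by enumerating all blocks, against 50% by chance: see the table.

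**3. Bias** = 2e(2c − 1). For b = 4 and e = 0.05: 2 × 0.05 × (2 × 0.708 − 1) = 0.042, or 42% of the 0.10 target.

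**4. Type I error.** The standard error of the difference is 0.17 × √(2/40) = 0.038, so a bias of 0.042 is about 1.1 standard errors. The noncentral t gives 19.1% for b = 4. Simulation gives about 18%, because the shift also adds some variance.

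| Fixed block | Correct guesses | Bias, e = 0.05 | Type I error (simulated) |
|---|---|---|---|
| 2 | 75% | 0.050 | about 25% |
| 4 | 71% | 0.042 | about 18% |
| 6 | 68% | 0.037 | about 15% |

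These rows assume that recruiters see the full counts of the list and act on every guess.

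**5. Varying the other assumptions**, with blocks of 4:
- One list serves both clinics, recruitment is equal and each clinic sees only its own counts: about 54% correct, bias 2 × 0.05 × 0.08 = 0.008, type I error about 6%.
- e = 0.025: bias 0.021, type I error about 8%.
- e = 0.05, acting only on certain assignments: bias 0.033, type I error about 13%.
- t-test on change scores, with the same shift at baseline and follow-up: the shift cancels, about 5%.
- Nobody acts on guesses: 5%.

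**6. Effect of the remedy** (e = 0.05, full counts visible). Randomly varying blocks of 4, 6 and 8 cut certain assignments from 33% (fixed blocks of 4) to about 2%. Correct guesses stay at about 68%, bias at about 0.036 and type I error at about 14%. Adding adjustment for baseline QoL, with an assumed baseline–outcome correlation of 0.5 and the same shift at both times, removes roughly half of the bias. Type I error is then about 8%; a check gave this both for fixed blocks of 4 and for the varying blocks.

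**The case against.** The strongest reply is that this is a reporting gap. Nothing in the protocol says that the clinics hold the envelopes or that staff see every allocation. Omitting the block size from a protocol that staff read is good practice, since printing it would make prediction easier. With two clinics on one list, each clinic's own counts say little. The ±0.05 shift has no source: it needs every recruiter to act on every guess in one direction, and to pick by future QoL when the stated criterion concerns attendance. Consent precedes assignment, and the later offer of NF to controls weakens the motive to steer. Baseline QoL-10 would reveal an imbalance, and change scores could largely cancel it.

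Much of this stands. A reader might infer that the clinics keep the envelopes, or that the trial's real type I error is 15–25%. The documents support neither: custody is unstated, and those figures are the upper part of a range that reaches down to 5%. Nor need selection favour NF; steering the other way would bias the comparison against it.

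What does not fall away is that none of these safeguards closes the two routes. Consent before assignment does not stop a clinician from timing when a patient is approached. Visible baseline imbalance shows a problem without preventing it. The method that is stated (envelopes prepared in advance, block design, open treatment, discretionary entry) can be replaced cheaply by a better one, so this is more than a request for detail.

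**Conclusion.** The point holds as an unexcluded risk of selection at entry, not as demonstrated bias. Its size rests on assumptions that the protocol does not settle: block size, who sees the counts, whether the clinics share a list, which scores the t-test compares, and whether anyone acts on a guess. Under the assumptions shown, type I error runs from 5% to about 25%, with about 18% for fixed blocks of 4, fully visible counts and a ±0.05 shift.

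A reader might also infer that external release with varying blocks settles the matter. It does not. It removes envelope tampering and nearly all certain knowledge, but a guess made before the patient is logged remains possible, and varying blocks are guessed about as well as fixed blocks of 6. That is why the analysis needs attention as well as the allocation. The change should be made before recruitment starts.

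**What to change.** In section 2, Experimental design, replace the allocation sentence with text that states:
1. The external researcher already in the plan holds the list and releases one assignment at a time, only after eligibility, consent and the baseline inventory have been irrevocably logged for that study number. No envelopes are kept at the clinics.
2. Block sizes vary at random (for example 4, 6 and 8) and are not disclosed to clinic or project staff.
3. Whether there is one list or one per clinic.

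In Statistics, compare the groups on follow-up QoL-10 with adjustment for baseline QoL-10 (analysis of covariance) in place of the unadjusted t-test. The baseline score is already collected, so this needs no new data. It reduces the residual risk but does not abolish it; the 8% figure depends on the assumed correlation of 0.5 and an equal shift at both times.

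Cost: a few sentences, a regenerated list, a short wait for each release and slightly looser balance between arms. With 100 patients over a two-year inclusion period (about 104 weeks), the load is about one message a week.

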When neurofeedback was introduced and implemented as an adjunct treatment in our out-patient addiction clinic in 2011, many patients reported positive effects on a variety of comorbid symptomatology, and the retention rate for those who received the treatment was also significantly higher than the norm for this patient group. These observations were confirmed in a pilot study conducted at the clinic in 2012, in which the treatment was also rated positively by the patients [16]. Furthermore, data from subsequently admitted patients, measured by the same tools as in the pilot, have shown generally the same trajectory. These findings have spurred a motivation to conduct a larger, randomized controlled study to further investigate the role of NF in the treatment of SUD, this time with focus on its add-on effects to the treatment as usual (TAU) regime. Recognizing the high cost of treatment failure for society as large, as well as the high emotional cost for the individual, we wish to investigate whether the physiological effects of the treatment will help elicit positive emotional states which can strengthen coping behavior and aid patients in their efforts to become and remain abstinent. Thus, we believe that NF can play an important role in a relapse prevention paradigm and that its contribution can be captured with global patient-reported outcome measures such as well-being and QoL.

The current research proposal departs from previous studies in four important areas:

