3. Accordingly, the theoretical framework for this study will be to use NF as a strategy and potential tool in relapse prevention. Negative emotional states, such as anger, anxiety, depression, frustration, and restlessness are associated with higher rate of relapse to drug use [20]. By closely monitoring these variables throughout the project, we will be able to assess whether NF has a potential add-on effect on the patient's ability to cope with such negative emotions and the ensuing drug urge and cravings.

4. The proposed design has a stronger user involvement than previous research efforts in the field. User representatives with personal experience with NF will take an active part in the intervention and have regular dialogue meetings with participants, allowing informal exchanges about the method (e.g., possible effects and side-effects). We expect this element of the study to potentially boost the effect of the intervention. This way of boosting effects of other interventions has recently become a recommended strategy in the addiction treatment field [21].

Approaches, hypotheses, and choice of method

The overall aim of the study is to acquire more knowledge about the effectiveness of NF in the treatment of substance use disorders in general, specifically in relation to its effect on physical and psychological distress (e.g. sleep disturbances, anxiety symptoms etc.), and subsequently on its ability to improve QoL and prevent relapse. An RCT study will be undertaken to examine whether neurofeedback (NF) + treatment as usual (TAU) compared to TAU only can increase the QoL of patients with a SUD in the short and long term. We hypothesized that, compared to the TAU condition the NF + TAU condition would result in higher QoL at the end of treatment as well as at a 3- and 12-month follow-up. Included in our QoL assessment measure is perceived functioning in important areas such as work and social relations.

Our secondary outcome hypothesis is that the NF+TAU condition will result in better substance use outcomes as well as improvement in sleep quality, psychological distress, and symptoms of anxiety and depression at the end of treatment and at follow-up compared to controls. Drop-out rates will also be compared for the two groups, controlling for baseline demographic and severity variables.

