 - Mental distress will be measured with the Symptom Check List-10 (SCL-10). This scale is a 10-item index with a four-point response scale that maps anxiety and depression. It is an abbreviated version based on the more comprehensive SCL-90, and has been shown to be valid indicators of psychological distress. The corresponding cut-off point to the conventional 1.0 for SCL-90 is 1.85 [26, 27].
 - Restlessness and trepidation, measured with a visual analogue scale (VAS) on which the respondents are asked to rate their level of uneasiness from “none” to “very high” on a 10 cm, unmarked horizontal line [28, 29].
- Substance use:
 - Measured by selected questions from the European version of the Addiction Severity Index (EuropASI), a multi-dimensional interview used to measure a variety of aspects related to substance use [30].
 - Measured with two visual analogue scales (VAS), one for alcohol consumption and one for drug use, on which the respondents are asked to rate their intake in the last week by inserting a mark on a 10 cm, unmarked horizontal line [28, 29].
 - Perceived severity of substance use: As the study includes persons with both alcohol and drug dependence, we will also include a short, overall substance use severity measure at baseline; the Survey of Readiness for AA Participation (SYRAAP) severity subscale [31].
- Physiological variables:
 - Sleep quality, measured with a visual analogue scale (VAS) on which the respondents are asked to rate their sleep quality from “worst perceivable” to “best perceivable” on a 10 cm, unmarked horizontal line [28, 29].
- Cognitive function:
 - Measured with the Montreal Cognitive Assessment (MoCA), a brief screening instrument sensitive to mild cognitive impairment. The scale samples behavior across 14 performance tasks that engage multiple cognitive domains including attention, language, visuospatial, executive, and memory. Total possible score is 30 points, and a score of 26 or greater is classified as within normal range, that is, without evidence of cognitive impairment [22].
 - Measured with the QIK test – a continuous performance test devised to yield a reliable pre-post measure on attentional variables. It is a go/no-go challenge test, known as a choice reaction time test. It measures speed, accuracy and consistency and compares data to norms.

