- To assess the *trajectories of change* in the NF-TAU condition, a simple computer-based screening test will be administered weekly to each participant during the project period, measuring: a) alcohol and drug use, b) sleep quality, c) restlessness and trepidation and d) perceived functioning (ORS). These VAS scales have been described above.

The participants will be reassessed after treatment and at a 3- and 12- month follow-up period. Research assistants (RAs) blinded to the patient’s condition assignment will conduct the follow-up interviews. Efforts will also be made to examine non-completers. Respondents will be reimbursed NOK 250 (\$30) for completing the follow-up interviews.

Sample size calculation

Sample size calculation is based on a previous study of a similar population where patients had a mean QoL score at 0.57 (SD 0.17) [32]. A minimal clinical relevant improvement and between group difference is considered to be 0.10 [33]. A sample size of 40 in each group has an 80% power to detect a 0.10 mean difference between groups with a significance level (alpha) of 0.05 (two-tailed). The power calculation was carried out with StatMate ver. 2.0 (GraphPad Software, Inc., San Diego, CA, US). We expect a 20% attrition rate at follow-up, thus, 50 patients will be needed in each group.

Statistics

Baseline variables will be reported with descriptive statistics. Difference between randomized groups on primary outcomes will be assessed with Student's t-test. Secondary outcome will be assessed with appropriate tests, e.g., the weekly repeated measures will be analyzed with generalized estimating equation (GEE) to test for differences between groups.

3. The project plan, project management, organization and cooperation

Project group:

- Principle investigator and PhD supervisor: [name] PhD, Addiction Unit (ARA), Sørlandet Hospital HF (SSHF)
- Assistant supervisor: [name] MD/PhD: ARA, SSHF and University of Oslo
- Statistical supervisor: [name] PhD: Oslo Centre of Biostatistics and Epidemiology, Oslo University Hospital
- User representative: [name]
- Clinical neurofeedback specialist, [name], ARA, SSHF

Advisory board:

The advisory board consists of national and international specialists on neurofeedback and QEEG [34, 35]. In addition, we cooperate with a community based researcher who is our link to the local municipality [36].

- [name], Clinical Director, London Scientific Neurotherapy

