At least six scientific papers are planned to be written, three of which will form the basis for a PhD dissertation, and three for the post-doc position. All are intended to be published in international peer-reviewed journals, such as *Substance Abuse Treatment, Prevention, and Policy*; *Addiction Science & Clinical Practice*; *Journal of Psychiatry and Neuroscience*, and *Applied Psychophysiology and Biofeedback*. The results will also be communicated in relevant national and international research arenas and targeted to decision makers in the addiction and health fields, as well as to the existing clinical network and their associated websites and social media sites. Moreover, the results will be used to expand and improve the practice of neurofeedback for the addiction population by providing further documentation of its effectiveness.

Tentative titles for the papers are as follows:

1. "Feasibility and effectiveness of neurofeedback in substance use treatment: Experiences from a naturalistic pilot study"
2. "Clinical effectiveness of neurofeedback in a mixed substance abuse population as measured by quality of life. A randomized controlled trial"
3. "Do effects last? Follow-up results 12 months after completing a neurofeedback intervention program for substance use disorders"
4. "Can neurofeedback reduce psychological distress in patients with substance use disorders? Secondary outcomes of an RCT."
5. "Does cognitive function predict effectiveness of and treatment retention in a neurofeedback treatment regime?"
6. "Hangin' in there: Can neurofeedback reduce drop-out rates and prevent relapse in addiction treatment? Assessment of costs and benefits."

Communication with users

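### Preventing relapse is a stated aim, but no described measure is shown to capture return to use between the follow-up interviews, and entry does not require abstinence

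*Combined protocol and SAP*

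**What the plan says.** **Aim.** Section 2, Approaches, hypotheses, and choice of method, says the trial will study the effect of neurofeedback on distress and "subsequently on its ability to improve QoL and prevent relapse". The list of tentative papers in section 4 includes one that asks "Can neurofeedback reduce drop-out rates and prevent relapse in addiction treatment". The formal secondary hypothesis is worded differently: "the NF+TAU condition will result in better substance use outcomes as well as improvement in sleep quality". No section defines relapse as an event, gives a threshold for it, or says who is at risk of it.

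**Entry.** Experimental design makes patients clinically eligible "after having achieved an initial level of stable attendance at the clinic" and links this to the relapse-prevention focus. Neither the inclusion nor the exclusion criteria mention abstinence. Background and status of knowledge says the treatment is meant to "aid patients in their efforts to become and remain abstinent", which covers both kinds of patient.

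**Measures.** Under Instruments, substance use has two repeated sources. The first is "Measured by selected questions from the European version of the Addiction Severity Index (EuropASI"), with neither items nor recall period named. The second is a pair of visual analogue scales (VAS), one for alcohol and one for drugs, on which patients "rate their intake in the last week by inserting a mark on a 10 cm, unmarked horizontal line". All participants complete the inventory at the outset. They are reassessed after treatment and at 3 and 12 months, and blinded research assistants conduct the follow-up interviews.

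**Weekly testing.** The use scales are also part of a weekly computer test, introduced as a way to follow change: "in the NF-TAU condition, a simple computer-based screening test will be administered weekly to each participant during the project period". Statistics plans a GEE (generalized estimating equation) analysis of the weekly data to compare the groups.

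**The concern.** Relapse is an event in time. To claim that an intervention prevents it, the trial must observe whether a return to use happened at any point in the period of interest, and must know who was abstinent when that period began.

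A one-week look-back at a visit shows current use. A patient who returned to use in month 5 after treatment and stopped in month 10 would show no use on the month-12 scale. Unless the EuropASI questions reach back far enough, or weekly testing is still running, nothing described would record that episode.

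The mixed entry population raises a second problem. For a patient abstinent at baseline, the question is whether abstinence lasts. For a patient still using, it is whether use stops or falls. One rate across both answers neither question, and its value depends on the mix at entry.

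At stake is the interpretation of the relapse aim and of the planned relapse paper.

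**Working it through.** The plan gives no figure for relapse or for detection of use, so there is none to reproduce. Its sample size rests on quality of life and does not bear on this point.

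**Inputs**
- VAS look-back: 1 week (Instruments).
- Visits: end of treatment, 3 months, 12 months (Instruments).
- Intervention: 5 months (Experimental design), or 5 × 52/12 = 21.7 weeks.
- Follow-up clock: 12 months from completing the intervention, taken from the title of planned paper 3; 52 weeks or 365 days.
- EuropASI recall: not stated; 30 and 90 days are assumed to show a range.

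**Step 1. Share of follow-up covered by the visit windows.** Coverage = (number of windows × window length) / 365 days.

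| Source at the 3- and 12-month visits | Calculation | Coverage |
|---|---|---|
| VAS, 7 days | 14/365 | 3.8% |
| EuropASI if 30 days (assumed) | 60/365 | 16% |
| EuropASI if 90 days (assumed) | 180/365 | 49% |

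**Step 2. Effect of weekly testing.** Consecutive one-week look-backs, if completed, leave no gap. From start of treatment to month 12 of follow-up is 21.7 + 52 = 73.7 weeks.
- Weekly scale ends with treatment: (21.7 + 2)/73.7 = 32% overall, made up of 100% during treatment and 2/52 = 3.8% after it.
- Weekly scale runs to month 12: 100%.

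**Step 3. Coverage is not detection.** A long episode can overlap a short window. Suppose an episode of *d* weeks starts at a uniformly random time in the 52 follow-up weeks, and the VAS windows are weeks 12–13 and 51–52. For *d* up to 12, the chance that a window catches it is 2(1 + *d*)/52. From 12 to 38 weeks the earlier window's catchment is capped at 13 weeks, giving (14 + *d*)/52.

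| Episode length | Calculation | Caught by the VAS at the two visits |
|---|---|---|
| Negligible | 2/52 | 3.8% |
| 4 weeks | 10/52 | 19% |
| 8 weeks | 18/52 | 35% |
| 12 weeks | 26/52 | 50% |
| 26 weeks | 40/52 | 77% |
| 39 weeks or longer | – | 100% |

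The documents give no distribution of episode lengths, so these are a range, not an estimate.

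**Step 4. Arms and duration of the weekly test.** The sentence introducing it refers to the neurofeedback arm, then to every participant. The GEE comparison needs weekly data in both arms, which favours the wider reading. The period over which it runs is named but not defined. If the test were given in one arm only, return to use would be observed more closely in that arm, and a comparison built on it would be biased.

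**The case against.** The strongest case against has four parts.

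1. **Weekly testing.** It is in the protocol, it covers the period in which it runs, and it dates use to the week. This stands for the treatment period, if both arms are tested, and for follow-up if the test continues to month 12. The protocol settles neither condition.
2. **EuropASI.** It is listed ahead of the VAS as a use measure. A reader might infer that the one-week scale is the only use measure; it is not. It is the only one with a stated recall period.
3. **Missed relapses and power.** A reader might infer that most relapses would go unseen, or that a relapse comparison would lose a calculable amount of power. The documents support neither. Step 3 shows that detection depends on episode length, and EuropASI could add to it. The relapse figure of more than 80% in section 1 refers to cessation attempts across substance classes, not to stably attending outpatients on usual treatment, and the probability of detection is not given anywhere.
4. **Role of relapse.** Quality of life is primary, and the secondary hypothesis concerns substance use outcomes, which current-use measures do address. This limits the consequence, but relapse remains in the aim and in a planned paper.

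A reader might also infer that patients using at entry cannot relapse. That presumes one definition. A return to heavier use could be defined for them; the protocol does not do so.

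**Conclusion.** The point holds in a limited form. The trial intends to speak about preventing relapse, but the described measures are not shown to record return to use between the follow-up interviews, and one rate would mix two populations with different goals.

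If weekly testing ends with treatment, the VAS covers 2 of 52 follow-up weeks, about 4%. That figure assumes the follow-up clock starts at the end of treatment and says nothing about EuropASI, whose recall is unstated. If weekly testing runs to month 12 in both arms and is completed, the coverage gap closes. The missing definition and the mixed entry population remain either way.

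This is a cheap improvement to a secondary aim. It does not affect the primary analysis.

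**What to change.** 1. In the blinded 3- and 12-month interviews already planned, ask about the whole interval since the last interview: any use of the problem substance, date of first use, and number of using days or months.
2. Use the substance-use data already collected at baseline to classify patients as abstinent or using at entry, state the rule, and report the two groups separately.
3. State that the weekly VAS is given to both arms, and for how long.
4. If these changes are not made, reword the aim from preventing relapse to current substance use.

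The cost is a few interview questions and amendment wording. There are two downsides. Recall over up to 9 months, the gap between the last two interviews, is imperfect. The abstinent-at-entry group will also be smaller than the full sample, by an amount the documents do not let us estimate, so its results should be treated as descriptive.

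### Forty analysed patients per group give 74% power on the plan's own inputs, not the stated 80%; reaching 80% takes 47 per group

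*Combined protocol and SAP*

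**What the plan says.** The whole calculation sits in one paragraph, Sample size calculation, in section 2 of the combined protocol and SAP.

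- Variability comes from an earlier study in a similar population, where "patients had a mean QoL score at 0.57 (SD 0.17").
- The target effect is fixed on clinical grounds: "A minimal clinical relevant improvement and between group difference is considered to be 0.10".
- The power claim reads: "A sample size of 40 in each group has an 80% power to detect a 0.10 mean difference between groups with a significance level"; the level is then set at 5%, two-sided.
- The recruitment target follows: "We expect a 20% attrition rate at follow-up, thus, 50 patients will be needed in each group".

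The next paragraph, Statistics, assigns the primary outcome to Student's t-test. Neither paragraph mentions baseline adjustment, a correlation between baseline and follow-up, or any other SD. The software is named, but its inputs and output are not shown.

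**The concern.** The paragraph gives enough to check the claim, and the claim fails the check. A difference of 0.10 against an SD of 0.17 is a standardised difference of a little under 0.6. Forty per group is too few to detect that with 80% power at a two-sided 5% level.

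Two things depend on the figure. First, it is the stated power for the primary outcome, quality of life, at the effect the plan itself regards as the smallest worth having. Second, the recruitment target of 50 per group is built on the 40, so the error carries forward. The statement in section 3 that the required number can be recruited within two years was made for that uncorrected target. A reader who takes the 80% at face value would also give a null result more weight than the design supports.

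**Working it through.** **Inputs.** From Sample size calculation: SD σ = 0.17, difference δ = 0.10, two-sided α = 0.05, n = 40 analysed per group, attrition 20%. From Statistics: Student's t-test. Equal allocation is taken from the equal group sizes.

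**Step 1: trying to reproduce the stated 80%.**

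Standardised difference: δ/σ = 0.10/0.17 = 0.588.

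Noncentrality parameter: δ / (σ√(2/n)) = 0.10 / (0.17 × √(2/40)) = 0.10 / (0.17 × 0.2236) = 0.10 / 0.03801 = 2.63.

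- Exact, noncentral t with 2 × 40 − 2 = 78 degrees of freedom: power = **73.8%**.
- Normal approximation: Φ(2.63 − 1.96) = Φ(0.67) = **74.9%**.

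The stated 80% is not reproduced by either method. The type II error is 100 − 73.8 = 26.2%, against 20% implied.

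**Step 2: the number that does give 80%.**

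Normal approximation: n = 2 × [σ(1.960 + 0.842)/δ]² = 2 × (0.17 × 2.802/0.10)² = 2 × 4.763² = 45.4, so 46 per group.

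Exact t-test:

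| Analysed per group | Power |
|---|---|
| 40 | 73.8% |
| 45 | 78.8% |
| 46 | 79.7% |
| 47 | 80.6% |
| 50 | 83.0% |

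The smallest n that reaches 80% with the planned test is **47**.

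**Step 3: carrying it into recruitment.** The attrition step itself is sound: 40/0.80 = 50. Starting from 47, it gives 47/0.80 = 58.75, so **59 per group** (118 in total) against 50 (100 in total). Starting from 46, it gives 57.5, so 58 per group (116 in total).

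**Step 4: what would make 40 per group correct.** Using the exact t-test and changing one input at a time, 80% at n = 40 requires a difference of 0.108 instead of 0.10, or an SD of 0.158 instead of 0.17.

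**Step 5: alternative readings of the paragraph.**

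| Reading | Power at n = 40 |
|---|---|
| SD at its lower rounding limit, 0.165 | 76.3% |
| SD near its upper rounding limit, 0.1749 | 71.4% |
| One-sided α = 0.05 (the plan says two-tailed) | 83.2% |
| SD 0.165 and difference 0.105 together | 80.3% |

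Only the last row lands on 80%. It needs both inputs at the favourable edge of rounding, and 0.10 is a chosen relevance threshold, not a rounded estimate.

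**Step 6: baseline adjustment (assumption only).** With ANCOVA the working SD becomes σ√(1 − r²), where r is the correlation between baseline and follow-up. The documents give no value for r. Ignoring the one degree of freedom spent on the covariate, power at n = 40 is 77.7% for r = 0.30, 80.9% for r = 0.40 and 85.1% for r = 0.50. The crossing point solves 0.17√(1 − r²) = 0.1577, so r² = 1 − (0.1577/0.17)² ≈ 0.14 and r ≈ 0.37.

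**The case against.** The arithmetic is hard to dispute; the case on the other side is about its weight.

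- **The SD is inferred.** The paragraph says the calculation is based on a study with SD 0.17 but not in so many words that 0.17 was entered as the common SD. That is true, but it is the only SD given and the natural reading. If another was used, the paragraph is wrong for a different reason.
- **The gap is small.** It is about 6 percentage points of power, or a detectable difference of 0.108 instead of 0.100. Type I error, the effect estimate and its confidence interval are untouched. This stands, and it limits how serious the error is.
- **Attrition may be lower than planned.** Fifty per group are randomised and the 20% loss is an expectation. With 47 or more of 50 analysed (loss of 6% or less), power passes 80%; with all 50 it is 83.0%. This could soften the consequence, particularly at end of treatment, but the plan attaches 80% to 40 analysed, and that remains wrong.
- **Over-reading of a null result is a risk, not a stated intention.** The documents do not say that a null result will be interpreted through planned power. Fair; the point is that the published figure invites it.
- **ANCOVA could be back-solved.** Picking a correlation because it recovers 80% would be circular, and switching to ANCOVA replaces the planned primary test. This stands: that route needs a justified correlation and an amended Statistics paragraph.

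**Conclusion.** The concern holds. On the plan's own inputs and test, 40 analysed patients per group give 74% power for a difference of 0.10, not 80%. The required number is 47 analysed and 59 randomised per group, against 40 and 50. By the normal approximation the figures are 75% power, 46 analysed and 58 randomised, which leads to the same conclusion.

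This rests on 0.17 being the common SD, equal allocation, and an unadjusted two-sided t-test at 0.05, all as the plan states or plainly implies. The shortfall is modest and does not bias the result, but a power statement for the primary outcome that its own inputs contradict should be corrected.

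**What to change.** Restate the power in the Sample size calculation paragraph, for example:

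> *Assuming an SD of 0.17, 40 analysed patients per group provide 74% power for a between-group difference of 0.10, and 80% power for a difference of 0.108, using a two-sided t-test at the 5% level.*

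This costs one sentence and no patients; the price is a less favourable stated power.

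If the sponsor wants to keep 80% for a difference of 0.10, there are two routes:

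1. **Raise the sample** to 47 analysed, 59 randomised per group. That is 18 more patients in total (118 − 100), and the feasibility statement in section 3 would need to be reassessed.
2. **Keep 40 analysed and plan a baseline-adjusted primary analysis (ANCOVA).** Quality of life is already collected from everyone at the outset, so no new data are needed. The Statistics paragraph must change accordingly, and the assumed correlation must be stated and justified from data. It needs to be about 0.37 or higher; at 0.30 the power would be about 78%.
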